## **12 EXPOSURE AND COMPLIANCE**

Exposure and compliance will be descriptively summarized for the SAF.

### **12.1 Exposure**

Exposure will be displayed for both treatment periods as the number of subjects receiving 1,2,3 or 4 infusions. It will be descriptively summarized. For percentage calculation, the denominator will

be the number of subjects in the FAS for the Treatment Period A. For the Treatment Period B, the denominator will be the number of subjects treated in Treatment Period B.

In addition, 2 further overviews will be generated.

First the number of subjects with a planned reduced dose will be summarized. Those subjects are identified if the eCRF entry “Volume of drug transferred into the infusion bag” is not 8 mL. Denominator usage as described above.

Secondly, the number of subjects with a completely and not completely administered dose will be displayed. The display will be done by day for Treatment Period A (Day 1, Day 4, Day 7, Day 10) and visit for Treatment Period B (Visit 11, Visit 12, Visit 13, Visit 14). For percentage calculation, the number of subjects with an administered drug for that day/visit will be used.

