10.2 Administration of investigational medicinal products

For subjects with no or mild renal impairment, the full contents of a single vial (8 mL) will be diluted in 500 mL normal saline and administered by slow intravenous infusion (240 minutes [maximum 260 minutes]) at Visit 2, Visit 3, Visit 4, and Visit 5, resulting in a total dose of 400 mg neridronic acid or matching placebo. The complete solution volume of 500 mL should be administered at each infusion visit unless treatment is suspended for safety reasons. Any administration of less than 500 mL should be noted and recorded in the eCRF. No more than 4 infusions (400 mg total dose) may be administered to any subject in Treatment Period A.

For subjects with no or mild renal impairment included in Treatment Period B, the full contents of a single vial (8 mL) will be diluted in 500 mL normal saline and administered by slow intravenous infusion (240 minutes [maximum 260 minutes]) at Visit 11, Visit 12, Visit 13, and Visit 14, resulting in a total dose of 400 mg neridronic acid.

A maximum total dose of neridronic acid 800 mg is planned for subjects allocated to neridronic acid in Treatment Period A who go on to complete Treatment Period B.

For subjects with moderate renal impairment, the following dose adjustments will be applicable:

CKD-EPI Stage 3a (eGFR 45 mL/min/1.73 m² to <60 mL/min/1.73 m²)

6 mL of solution from a single vial (corresponding to neridronic acid 75 mg) will be diluted in 500 mL normal saline and administered by slow intravenous infusion (240 minutes [maximum 260 minutes]) at each treatment visit, resulting in a total dose of 300 mg neridronic acid or matching placebo.

CKD-EPI Stage 3b (eGFR 30 mL/min/1.73 m² to <45 mL/min/1.73 m²)

5 mL of solution from a single vial (corresponding to neridronic acid 62.5 mg) will be diluted in 500 mL normal saline and administered by slow intravenous infusion (240 minutes [maximum 260 minutes]) at each treatment visit, resulting in a total dose of 250 mg neridronic acid or matching placebo.

Any decision regarding dose adjustment will be based on the last eGFR value available before Visit 2 for Treatment Period A and the last eGFR value available before Visit 11 for Treatment Period B.

All infusions must be performed at the trial site under the supervision of medical staff.

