11.1.2.4 Visit 5 (Day 10; ± 1 day)

The following evaluations will be performed prior to the start of IMP infusion:

- Record vital signs.
- Record triplicate 12-lead ECG (at least 15 minutes prior to the start of infusion).
- Record adverse events.
- Take blood for safety laboratory testing.
- Collect urine for quantitative urinalysis at the central laboratory.
- Perform dipstick urinalysis.
- Perform semi-quantitative dipstick urinalysis for urinary ACR.
- Perform a urine β -HCG pregnancy test.
- Compliance assessment for electronic diary.
- Check trial discontinuation criteria (for details, see Section 9.3.1).
- Check IMP suspension criteria (for details, see Section 9.3.2).
- Take blood for pharmacokinetic evaluation (see Section 1.7.1 for time point).

Once the above evaluations have been performed, the IMP will be administered (for details, see Section 10.2).

During the infusion, a blood sample will be taken for pharmacokinetic evaluation (see Section 1.7.1 for time point).

The following evaluations will be performed after the infusion:

- Record vital signs.
- Record triplicate 12-lead ECG (at least 15 minutes after the infusion).
- Record concomitant medications and therapies.
- Record adverse events.
- Take blood for pharmacokinetic evaluation (see Section 1.7.1 for time point).

11.1.3 Follow-up Period 1

In case of interruption or suspension of treatment, the first follow-up visit (Visit 6) should be scheduled at 4 days (± 2 days) after the last infusion visit. All subsequent visits must remain as originally scheduled relative to Visit 2 (e.g., Visit 7 occurs at 42 days [6 weeks] ± 3 days after Visit 2). No more than 4 infusions are allowed in Treatment Period A; any partial infusion (exceeding 20 mL) must be counted as 1 infusion.

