## 12.2 Compliance

Compliance will be assessed for each visit. Compliance (%) to IMP administration will be set to 100%, if the dose was completely administered. Otherwise, compliance (%) will be calculated as the ratio of the approximate value administered, divided by the planned dose (500 mL).

Moreover, the cumulative compliance per treatment period will be derived as the ratio of the actual cumulative dose divided by the planned cumulative dose.

Compliance and cumulative compliance will be descriptively summarized.

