#### **19.1.2.2 Protocol deviations**

Protocol deviations are based on the analysis dataset ADDV. Major protocol deviations are retrieved from the respective SDTM dataset (SDTM.DV.DVCAT). No further protocol deviations are programmed in the analysis datasets for ADDV (if not otherwise specified in the SAP).

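### SAP 12 infers the planned dose from the volume drawn up, so its planned-reduced count misclassifies 4 of 6 possible volume mismatches and its per-visit compliance detects none

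*SAP*

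**What the plan says.** **The plan for each subject (Protocol 10.2).** The volume of IMP per infusion depends on renal function: 8 mL with no or mild impairment, 6 mL in CKD-EPI Stage 3a (eGFR 45 to below 60) and 5 mL in Stage 3b (eGFR 30 to below 45). The deciding value is fixed too: "Any decision regarding dose adjustment will be based on the last eGFR value available before Visit 2 for Treatment Period A", and the corresponding value before Visit 11 for Period B. Protocol 10.1.3 has the volume put into each bag recorded in the eCRF.

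**Exposure (SAP 12.1).** "First the number of subjects with a planned reduced dose will be summarized". The rule for finding them is "Those subjects are identified if the eCRF entry “Volume of drug transferred into the infusion bag” is not 8 mL". It does not use eGFR or renal stage. Two other displays count infusions received (1 to 4) and complete versus incomplete administrations by day or visit.

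**Compliance (SAP 12.2).** "Compliance (%) to IMP administration will be set to 100%, if the dose was completely administered". When a bag is not fully infused, the visit percentage is the amount infused over a fixed denominator of 500 mL, which the SAP calls the planned dose but which is the bag volume. Cumulative compliance per period is the cumulative dose given over the cumulative dose planned, with no unit and no planned value by renal stage.

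**The concern.** A table headed as planned dose should rest on the plan. Here the plan is read off the execution, so the two cannot disagree: whatever was drawn up becomes what was intended. The compliance percentage is the next place where a wrong volume might show, but its numerator and denominator are both bag volume, so the amount of IMP in the bag drops out.

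This matters for two descriptive purposes. Protocol 8.2 names dose and infusion time as the main factors in renal toxicity and relies on dose adjustment in moderate impairment. The objectives concern a cumulative dose of 400 mg, and Protocol 6.3 reports that a total of 250 mg did not separate from placebo in an earlier trial. A reader of the trial report would look to the exposure section for how many subjects received the dose the protocol assigned them, and SAP 12 has no row that answers this.

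**Working it through.** **Inputs.** Vial: 100 mg neridronic acid in 8 mL (Protocol 10.1.1, 10.1.3). Planned volumes: 8, 6 or 5 mL (Protocol 10.2). Flag and compliance rules: SAP 12.1 and 12.2.

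**Step 1: reproduce the protocol's doses.** Concentration = 100 / 8 = 12.5 mg/mL.
- 8 × 12.5 = 100 mg; × 4 = 400 mg
- 6 × 12.5 = 75 mg; × 4 = 300 mg
- 5 × 12.5 = 62.5 mg; × 4 = 250 mg

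All agree with Protocol 10.2 and SAP 5.1.

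**Step 2: apply the SAP rules to every mismatch among 8, 6 and 5 mL, with all four bags complete.** Flag = transferred volume not 8 mL. Visit compliance = 100% for a complete bag. Received/planned = transferred mL / planned mL.

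| Renal stage (planned mL) | Transferred mL | SAP 12.1 counts as planned reduced? | Correct under Protocol 10.2? | SAP 12.2 visit compliance | Received/planned (mg over 4 infusions) |
|---|---|---|---|---|---|
| None/mild (8) | 6 | Yes | No | 100% | 75% (300/400) |
| None/mild (8) | 5 | Yes | No | 100% | 62.5% (250/400) |
| 3a (6) | 8 | No | No | 100% | 133.3% (400/300) |
| 3a (6) | 5 | Yes | Yes | 100% | 83.3% (250/300) |
| 3b (5) | 8 | No | No | 100% | 160% (400/250) |
| 3b (5) | 6 | Yes | Yes | 100% | 120% (300/250) |

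The flag is wrong in 4 of 6 rows: two falsely counted and two missed. In the other two it is right, because the subject did have a reduced dose planned, although the volume given was not the planned one. Visit compliance is 100% in all six, against 62.5% to 160% of plan.

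Taken literally, the rule also counts volumes that belong to no renal stage. A 7 mL entry for a subject with no or mild impairment is counted as planned reduced, at 7/8 = 87.5% of plan.

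**Step 3: incomplete bag.** Take a Stage 3b subject given 8 mL with 400 of 500 mL infused.
- SAP 12.2: 400 / 500 = 80%.
- Against plan: 8 × (400/500) / 5 = 6.4 / 5 = 128%.

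The SAP shows under-dosing where the subject received more than the protocol's planned amount.

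**The case against.** **These are descriptive tables.** The primary and secondary efficacy analyses use the FAS by allocated treatment and do not change. Renal safety is summarised directly through creatinine, eGFR and urinary albumin/creatinine ratio. This stands and limits the point.

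**As a count of reduced volumes given, the table is right.** A subject given 8 mL did not receive a reduced volume. That is true, but the table is specified as a count of what was planned, and relabelling it would still leave planned and transferred volume uncompared.

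**Cumulative compliance might be computed in mg.** No unit is given, so this reading is open, and it would be too strong to say that compliance is measured only in mL of bag. But the only planned dose defined in Section 12 is 500 mL, so the measure is undefined for subjects on an adjusted dose.

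**A dosing error may surface elsewhere.** Major deviations are tabulated overall and by site (SAP 10.3), and collected data are listed. SAP 19.1.2.2 says "No further protocol deviations are programmed in the analysis datasets for ADDV", but that does not exclude checks upstream; Protocol 13.4 refers to a Data Validation Plan that is not among these documents. This stands: an error is not necessarily lost, but showing it depends on its being recorded as a deviation or found in a listing.

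**Near-empty infusions.** A reader might infer that the infusion count hides these, because Protocol 11.1.3 says "any partial infusion (exceeding 20 mL) must be counted as 1 infusion". The documents do not support that. An infusion stopped at about 20 mL appears as incomplete in SAP 12.1, has visit compliance of 20/500 = 4%, and takes the subject out of the Treatment Period A completers as defined in SAP 8.2.2.

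**Conclusion.** The derivation rule in SAP 12.1 is wrong for what it claims to count, and per-visit compliance in SAP 12.2 cannot register a volume error. Among the three protocol volumes, 4 of 6 mismatches are misclassified and all 6 show 100% when the bag is complete, at 62.5% to 160% of plan. Cumulative compliance is underspecified.

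This assumes that the eCRF entry holds the volume actually drawn up, as Protocol 10.1.3 describes, and that the plan is the one set by the protocol's own eGFR rule. The percentages are per-subject consequences of hypothetical errors. The documents give neither the number of subjects with eGFR below 60 nor an error rate, so the number affected cannot be computed.

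Two stronger conclusions do not follow. A reader might infer that the tables would certify correct renal dosing where it had failed; no SAP 12 table crosses eGFR with dose or makes that claim. A reader might also infer that every volume error leads to a wrong flag; a Stage 3b subject given 6 mL is correctly counted as having a reduced dose planned, and only the compliance figure misses the error.

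The effect is confined to descriptive exposure and compliance tables, but the fix is cheap enough to make.

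**What to change.** **SAP 12.1.** Derive the planned volume per treatment period (8, 6 or 5 mL) by the rule already in Protocol 10.2, from the last eGFR value available before Visit 2 and before Visit 11. Keep the word *available*: a result from a sample drawn earlier but reported after dosing should not turn a protocol-compliant volume into an apparent error. Count planned reduced dose on the derived value, and add a row for transferred volume above or below plan.

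**SAP 12.2.** Define compliance, per visit and cumulatively, as

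(volume of IMP transferred × fraction of bag infused) / planned IMP volume,

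with numerator and denominator summed over the period's planned infusions for the cumulative figure. As a volume ratio it works in both arms; mg received can be shown as well for neridronic acid at 12.5 mg/mL.

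**Cost.** SAP wording and one or two derived variables. eGFR, transferred volume and any infused volume below 500 mL are already collected (Protocol 12.4.5, 10.1.3, 10.2). Some subjects may show compliance above 100%, which needs a footnote. No dose or clinical rule changes.

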## 12.2 Compliance

Compliance will be assessed for each visit. Compliance (%) to IMP administration will be set to 100%, if the dose was completely administered. Otherwise, compliance (%) will be calculated as the ratio of the approximate value administered, divided by the planned dose (500 mL).

Moreover, the cumulative compliance per treatment period will be derived as the ratio of the actual cumulative dose divided by the planned cumulative dose.

Compliance and cumulative compliance will be descriptively summarized.

## 13 EFFICACY ANALYSES

### 13.1 Primary endpoint

#### 13.1.1 Average pain intensity (recorded in the eDiary)

The primary efficacy variable is the change from baseline to Week 12 in the average pain intensity score. The average pain intensity score is calculated as the weekly average of the pain intensities recorded daily (in the evening) in the electronic diary with a 24-hour recall period.

The average pain intensity score for Week  $x$  is based on the respective 24-average pain intensity scores recorded daily in the electronic diary during week  $x$ , i.e. 7-day intervals starting Day 1 to Day 7 for Week 1, and Day 8 to Day 14 for Week 2, etc.

For the average pain intensity score for Week  $x$ , all available values in Week  $x$  will be used, no imputation will be done for missing scores. If no pain scores are available for a week, the weekly mean for that patient and week will remain missing. E-Diary data beyond Day 84 will not be used for the analysis but be part of the subject data listing. Subjects in the FAS without baseline value and subject without any weekly average pain intensity subject be imputed with zero as change from baseline and for the baseline value imputation will be done as the average baseline value of the treatment arm.

Baseline is calculated as the mean of the average pain intensity score recorded daily in the electronic diary during the baseline phase (Day -7 to Day -1).

---

### 13.1.2 Main analysis

For the primary objective of the trial, the primary estimand is the difference in means of the primary efficacy endpoint of 400 mg intravenous neridronic acid compared to placebo for all allocated and treated subjects. This treatment policy or de facto estimand measures the effect of neridronic acid regardless of adherence to treatment or protocol.

The primary estimand will be estimated by the analysis of the primary efficacy endpoint for the Full Analysis Set. The primary analysis will fit a mixed model repeated measurement (MMRM) to the change from baseline in the average pain intensity scores from Week 1 to Week 12 recorded once daily in the electronic diary, including the covariate baseline pain intensity score, and the factors geographic region, week, treatment, and treatment-by-week interaction as fixed effects, and subject as random effect. An unstructured covariance matrix will be used to model the covariance structure, degrees of freedom will be estimated using the Kenward-Roger approximation.

The primary efficacy analysis will be performed using the contrast, i.e., the mixed model Wald test, of neridronic acid 400 mg versus placebo at Week 12 of the treatment, week and treatment-by-week interaction term of the mixed effects model described above. Model-based parameter estimates (least square means), standard errors, 95% confidence intervals, and p-values will be tabulated. This analysis will be performed using only the observed values without imputation of missing values.

If the default Newton-Raphson algorithm used by statistical analysis software (SAS) PROC MIXED fails to converge, the Fisher scoring algorithm up to iteration 2 will be used (via the SCORING=2 option of the PROC MIXED statement) to obtain the initial values of covariance parameters (Mallinckrodt et al. 2008). If this alternative also fails to converge, then in addition the no-diagonal factor analytic structure (via the TYPE=FA0(T) option of the REPEATED statement, where T=12 is the total number of weeks in the 12-week trial period) will be used, which effectively performs the Cholesky decomposition of the covariance matrix and is numerically more stable. The first algorithm that leads to convergence in this sequence of fallback measures will be the algorithm used for the primary analysis of the trial.

A descriptive summary of the weekly averages and the changes from baseline will be generated by treatment group.

A graphical plot of the model-based estimates and the 95% CI of the change from baseline of the average pain intensity scores over the 12-week trial period will be created. Both treatments will be presented in one plot by week.

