### **Sensitivity analysis**

Sensitivity analyses will be conducted with two imputation methods followed by an analysis of covariance (ANCOVA) model. The ANCOVA model will be fitted to the change from baseline in the average pain intensity scores at Week 12 recorded once daily in the electronic diary, with the covariate baseline pain intensity score, and the factors geographic region and treatment as fixed effects.

The results of the primary analysis and both sensitivity analyses will be summarized numerically and graphically in a forest plot, presenting the number of subjects, model estimates and 95% CIs of the treatment differences to placebo for both active doses.

The primary efficacy analysis will use the observed values of the primary efficacy endpoint without any imputations. To perform the sensitivity analyses for the primary analysis, weekly average pain intensities of the primary efficacy endpoint will be imputed until Week 12.

In the following the concept of PMM will be described as well as the details on the specific PMM imputation information for PMI and the delta shift method.

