#### *Delta Shift Method*

The Delta Shift Method is based on the observed distribution and shifts the observed means at the time points after dropout by a pre-specified value. In each pattern, the distribution of missing values

conditional on observed values is based on the shifted means, and imputations are drawn from the modified distribution. This approach models a diminishing placebo effect after a subject drops out.

The sensitivity analysis will use different values for the shift parameter  $\Delta$ . Delta will start with 0 and be increased by 0.1 points until the tipping point has been reached. The tipping point is defined as the delta that must be added in order to overturn conclusions from the primary analysis from statistically significant to statistically insignificant. Starting with 0 enables to evaluate MI under the MAR assumption.

The shift parameter is constant, i.e., the same shift parameter will be used for all treatment arms, for all times after dropout, and for all patterns. Based on this, the imputation step will be performed as follows:

- a. Estimate  $M$  sets of parameters of the linear model. All  $M$  parameter datasets will be stored in an analysis dataset.
- b. Generate  $M$  completed datasets using the  $M$  sets of parameters from step 1.
- c. Modify the completed datasets by adding a shift  $\Delta$  to each imputed value. All  $M$  imputed datasets will be stored in an analysis dataset.

All missing values will be imputed in the same way, i.e., no differentiation between intermittent missing values and missing values after dropout is made.

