### **13.2.1 Average pain intensity (recorded on tablet computer)**

The change from baseline in the average pain intensity, recorded on the tablet computer, will be analyzed with an MMRM, including the covariate baseline pain intensity score, and the factors geographic region, week, treatment, and treatment-by-week interaction as fixed effects, and subject as random effect. An unstructured covariance matrix will be used to model the covariance structure.

The analysis will be performed using the contrast, i.e., the mixed model Wald test, of 400 mg neridronic acid versus placebo at Week 26 of the treatment, week and treatment-by-week interaction term of the mixed effects model described above. Model-based parameter estimates, standard errors, 95% confidence intervals, and p-values will be tabulated. This analysis will be performed using the observed values without imputation of missing values.

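### The MMRMs fit one baseline slope for all weeks; a baseline-by-week term is a cheap precision gain for the week tested, not a correction of a validity error

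*SAP*

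**What the plan says.** SAP 13.1.2 models the "change from baseline in the average pain intensity scores from Week 1 to Week 12" with terms given as "including the covariate baseline pain intensity score, and the factors geographic region, week, treatment, and treatment-by-week interaction as fixed effects". It adds that "An unstructured covariance matrix will be used to model the covariance structure". The confirmatory contrast is "neridronic acid 400 mg versus placebo at Week 12". Protocol 1.5.3.1 and 14.1.7.1.1 give the same fixed effects. No section of either document crosses baseline with week.

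For pain on the tablet computer, SAP 13.2.1 uses an MMRM with "the covariate baseline pain intensity score, and the factors geographic region, week, treatment, and treatment-by-week interaction as fixed effects", tested at Week 26. SAP 13.2.3 to 13.2.5 refer the allodynia, pressure-pain and edema analyses to a model similar to that one.

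The sensitivity ANCOVA in SAP 13.1.3 is fitted at Week 12 alone, after imputation, "with the covariate baseline pain intensity score, and the factors geographic region and treatment as fixed effects". It therefore has its own Week 12 slope. Of the delta-shift series the SAP says: "Starting with 0 enables to evaluate MI under the MAR assumption".

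**The concern.** The outcome is change from baseline. In Week 1, pain should still track the baseline diary mean closely, so the slope of change on baseline is near zero. As that correlation weakens, the slope moves away from zero, and by Week 12 it can be quite different. A model with one slope has to compromise. Generalized least squares gives most weight to the weeks with the smallest residual variance, which are usually early ones, so the slope applied at Week 12 owes little to the Week 12 data. The part of the baseline relationship it misses stays in the Week 12 residual variance.

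At stake is the standard error of the primary contrast, and of the four secondary contrasts that are tested if the primary succeeds. The margin is thin. The increase from 86 to 90 per arm is there to offset the futility look, and no dropout allowance is stated. A lesser issue is that the primary model and the Week 12 ANCOVA, which are shown in one forest plot, adjust for baseline differently.

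**Working it through.** **1. The plan's own figure.** Inputs from Protocol 1.5.1 and SAP 5.2: difference 1.0, SD 2.0, one-sided 2.5%, 90% power. Normal approximation: n = 2 × (1.960 + 1.282)² × 2.0² / 1.0² = 84.1, so 85 per arm. The noncentral t gives power 0.8999 at 85, 0.9032 at 86 and 0.9156 at 90. The stated 86 is reproduced, with no credit taken for baseline adjustment.

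**2. Formula.** Let b be the vector of true week-specific slopes, S the residual covariance given baseline, and 1 a vector of ones. In large samples the common slope is approximately

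c = (1ᵀS⁻¹b) / (1ᵀS⁻¹1),

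and the Week 12 residual variance becomes V12 = S12 + Var(baseline) × (b12 − c)². The loss is V12 / S12.

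**3. Modest drift (all inputs assumed).** Baseline SD is 1.5 (variance 2.25). Slopes run linearly over 12 weeks from −0.05 to −0.3 (A) or from −0.1 to −0.4 (B). SD 2.0 is taken as the unadjusted SD of the Week 12 change, so S12 = 4 − 2.25 × 0.3² = 3.7975 (A) or 4 − 2.25 × 0.4² = 3.64 (B). Residual SD is constant, or rises linearly from half its Week 12 value. Correlations are AR(1) 0.8 or 0.9, compound symmetry (CS) 0.5 or 0.7, or an equal mixture of AR(1) 0.9 and CS 0.5. Power uses the noncentral t with 178 df and noncentrality 1/√(2V12/90). Selected results:

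| Setting | c | V12 / S12 | Power, common slope | Power, by week |
|---|---|---|---|---|
| A, constant SD (any correlation) | −0.175 | 1.009 | 0.926 | 0.928 |
| A, rising SD, AR 0.9 | −0.077 | 1.030 | 0.921 | 0.928 |
| A, rising SD, CS 0.7 | +0.052 | 1.073 | 0.911 | 0.928 |
| B, constant SD (any correlation) | −0.250 | 1.014 | 0.935 | 0.938 |
| B, rising SD, AR 0.9 | −0.132 | 1.044 | 0.928 | 0.938 |
| B, rising SD, CS 0.7 | +0.022 | 1.110 | 0.913 | 0.938 |

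Example, last row: 3.64 + 2.25 × (−0.4 − 0.022)² = 4.041, and 4.041 / 3.64 = 1.110. Week 12's own weight in c was 8% to 33% with constant SD; with rising SD it was 9% at most and sometimes negative.

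**4. Wider range.** This covered 36 settings: baseline SD 1.2 to 1.8; correlation with baseline 0.9 at Week 1, falling to between 0.3 and 0.7 at Week 12; residual AR(1) 0.85 to 0.95; SD of Week 12 change 2.0. The variance ratio ran from 1.00 to 1.92 (median about 1.08). Power without dropout was 0.896 to 0.966 with a common slope and 0.916 to 0.994 by week. In some settings the common slope did worse than no baseline adjustment (0.916).

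**5. Simulation of both MMRMs.** 90 per arm, baseline SD 1.5, 400 to 800 trials per setting, region omitted, approximate t reference:

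| Correlation with baseline at Week 12 | Dropout | SE common / by week | Power common / by week |
|---|---|---|---|
| 0.5 | none | 0.291 / 0.288 | 0.934 / 0.939 |
| 0.3 | none | 0.286 / 0.264 | 0.938 / 0.961 |
| 0.3 | about 16% | 0.315 / 0.290 | 0.865 / 0.925 |
| equal slopes at all weeks | none | 0.269 / 0.270 | 0.955 / 0.955 |

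Mean estimates agreed between the two models. With no true effect, the common-slope model rejected in 0.025 of trials without dropout and 0.033 with about 18% dropout (400 trials, Monte Carlo SE about 0.008). The last row shows the price of the extra term when it is not needed: about 0.5% to 1% of variance.

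**The case against.** A baseline main effect is a legitimate pre-specified model, and it was kept when Protocol Amendment 01 reworded the sentence that defines the primary model. The documents contain nothing from which to size the loss, and in some settings there is none. All of this stands, and it limits the point to efficiency.

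Four stronger readings are tempting, and the documents do not support them.

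- A reader might infer that the model leaves the trial short of its planned 90% power. Inflation of 2%, 5% or 8% does give 91.0%, 90.2% or 89.4%, but only if SD 2.0 is the residual SD after correct baseline adjustment. The sample size sections do not say so, and 86 per arm reproduces without any covariate.
- A reader might infer bias or an inflated type I error. The simulations show no difference in bias, and the 0.033 is within Monte Carlo error of 0.025.
- A reader might infer that the different slopes spoil the comparison of the primary result with the run at delta = 0, and that the new term would repair it. The SAP says only that this run evaluates multiple imputation under MAR; it does not call it the counterpart of the primary model. The ANCOVA also has a Week 12-specific region effect and uses imputed data, so the two would still differ.
- A reader might infer that the tablet model omits the more reliable diary baseline. SAP 8.2.2 defines baseline for average pain as the 7-day mean, while SAP 13.3.1 takes the Visit 2 tablet value. Which of them is the covariate in SAP 13.2.1 is therefore unclear, but an omission is not shown.

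**Conclusion.** The point holds as an efficiency improvement. One baseline slope is imposed on all weeks in the primary and tablet MMRMs and in the models patterned on the latter, and weeks other than the one tested mainly determine it.

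Under modest drift the loss is about 1% to 11% of Week 12 variance. That corresponds to roughly 2 to 18 of 180 subjects (180 × 0.01/1.01 = 1.8; 180 × 0.11/1.11 = 17.8). Power before dropout then stays above the planned 90%, at about 91% to 93% against 93% to 94% with week-specific slopes. If the slopes are equal there is no loss. If the correlation with baseline falls sharply by Week 12, the loss is larger, and at the edge of the wider range common-slope power reached 0.896.

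All these sizes rest on an assumed baseline SD, slopes and correlations, and on reading SD 2.0 as the unadjusted SD of change. They were computed for the primary model only; no size was derived for the tablet, allodynia, pressure-pain or edema models.

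**What to change.** Before unblinding, add the baseline-by-week interaction as a fixed effect to the primary MMRM (SAP 13.1.2; Protocol 1.5.3.1 and 14.1.7.1.1) and to the tablet, allodynia, pressure-pain and edema MMRMs (SAP 13.2.1 and 13.2.3 to 13.2.5; Protocol 1.5.3.2 and 14.1.7.2). In the last three, state the term explicitly instead of leaving it to a similar model. Record the change in SAP 7.1 and in the protocol.

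The cost is 11 further fixed-effect parameters in the primary model (12 weeks minus 1), fewer in the visit-based models, and up to about 1% of variance if the slopes are in fact equal. The SAP sentence needs reopening in any case, because it still lists subject as a random effect, which the current protocol text for the primary model does not. The change also aligns the primary model's baseline adjustment with that of the Week 12 ANCOVA, though the region effect and the imputation would still differ.
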